9.5.2 Secondary Outcomes

Specific Aim 1: Determine whether a mind/body therapy (hypnotherapy) is as, or is more effective and durable, in treating urgency urinary incontinence (UUI) than a non-mind/body treatment (pharmacotherapy)

This Aim's primary outcome: will be to compare between group difference in change in UUI episodes at 2 months. Secondary outcomes will be to; determine whether a mind/body therapy (hypnotherapy) is as, or is more effective and durable, in treating urgency urinary incontinence (UUI) than a non-mind/body treatment (pharmacotherapy) comparing change in UUI episodes at 6 and 12 months as well as comparing between group changes in urinary frequency and pad counts recorded on 3 day voiding diaries at 2,6 and 12 months, difference in "cure" in UUI episodes (defined as complete resolution of UUI, i.e. 0 UUI episodes, on voiding diaries at 2,6 and 12 months) and "durable cure" (defined as complete resolution of UUI on all follow-up voiding diaries at 2, 6 and 12 months), differences in expectation attainment (i.e. between group differences in follow-up Expectation question) and differences in questionnaire change scores [OAB-q SF, ISI, Global (PPBC) questionnaire scores and change in sexual function based on PISQ-12 scores]. Additionally, we will evaluate the baseline occurrence of concomitant syndromes such as irritable bowel syndrome and painful bladder syndrome in this population of

women with UUI based on the medical history and CRADI-8 and IBS Module and IC questionnaires. We will explore whether there is a difference in pain and IC symptoms following treatment if there are sufficient numbers of women with bowel abnormalities and IC at baseline.

Specific Aim 2: Determine whether hypnotherapy treatment of UUI (urgency urinary incontinence) is associated with greater modification of brain activation and connectivity on functional MRI than that which occurs following pharmacotherapy.

Hypothesis 2.1. Patients with urgency urinary incontinence will exhibit increased activation within portions of the limbic cortex (anterior cingulate cortex and insula) during bladder distension relative to healthy controls. Patients will also exhibit an abnormal pattern of functional connectivity within the limbic system.

This Aims' secondary outcome will be to evaluate differences in brain activation of the limbic cortex and brain connectivity at baseline between women with UUI and normative controls.

9.6 Data Analyses

Specific Aim 1: Determine whether a mind/body therapy (hypnotherapy) is as, or is more effective and durable, in treating urgency urinary incontinence (UUI) than a non-mind/body treatment (pharmacotherapy)

Statistical Analysis: Improvement between hypnotherapy and controls will be compared at baseline and followup at 2, 6, 12 months. Because of the possibility that a number of subjects may be cured (i.e. report "0" urgency incontinence episodes) at follow-up on voiding diary, we will use a zero inflated Poisson (ZIP) generalized linear mixed model for the analysis and compare groups' urgency incontinence episodes. The ZIP model analysis is proposed because the data are expected to be relatively low counts with the potential of a large numbers of zeroes, particularly at 2 and 6 months, in excess of those allowed by the Poisson. Simple conversion to percent change will not correct the discrete nature of the data ("cures" become 100 percent change rather than 0 UUI count at 2 months), and standard least squares methods will not be appropriate. If there is no inflation at 0, i.e. standard Poisson regression is appropriate, then the associated log-linear model yields percent change as a natural parameter (by exponentiating the group effect). If there is significant inflation at 0, the confidence interval for percent change in the mean will be constructed by combining the two portions of the model with standard error estimated by the delta method, and checked via bootstrap methods. We will be able to derive mean UUI episodes as well as mean % change in UUI episodes following ZIP model analyses. All other parameters, which are normally distributed or continuous variables, will be compared using a linear mixed model analysis. It is unlikely that there will baseline differences between groups, given that this is a randomized controlled trial. If baseline differences between groups are found (e.g. incontinence duration, coexisting illnesses, prior treatment), appropriate variables will be added to the analysis as covariates. We will include pre-treatment patient expectations and hypnotic susceptibility as covariates in the analysis and determine if they are independent predictors of treatment response. We will not exclude subjects based on hypnotic susceptibility to increase the generalizability of our findings. We anticipate subjects' pre-treatment expectations will be an independent predictor of improvement in urgency incontinence & guestionnaire scores (the previously determined sample size is adequately powered to find a relatively small partial R² of .05¹³ between expectations and outcomes). The primary outcome measure will be change in UUI episodes from baseline to follow-up with a between group comparison, and not "cure". However, the term "cure" may be used for secondary analyses. As such, our definition of "cure" will be: absence of UUI episodes recorded on voiding diaries at 2, 6 and 12 month follow-up. Primary analyses will be performed using intention to treat. A per protocol analysis will also be performed; those who did not comply with the study interventions, extensively used other concomitant treatments known to improve UUI (e.g. used other UUI medications, underwent sacral neuro-modulation), or missed multiple treatment sessions will be considered to have been off protocol subjects. Similar analyses will be performed comparing group differences in change in questionnaire scores while accounting for covariates such as pain/interstitial cystitis (based on VAS pain scale and IC questionnaire) or bowel abnormalities (based on the CRADI-8), medical history and demographic variables (based on the medical history and demographic sheets) on the outcomes.

Specific Aim 2: Determine whether hypnotherapy treatment of UUI (urgency urinary incontinence) is associated with greater modification of brain activation and connectivity on functional MRI than that which occurs following pharmacotherapy.

Hypothesis 2.1. Patients with urgency urinary incontinence will exhibit increased activation within portions of the limbic cortex (anterior cingulate cortex and insula) during bladder distension relative to healthy controls. Patients will also exhibit an abnormal pattern of functional connectivity within the limbic system.

Hypothesis 2.2. Among patients with urgency incontinence, hypnotherapy will decrease hyper-activation of the limbic cortex in response to bladder distension and/or modulate functional connectivity within the limbic system. Moreover, normalization of hyper-activation and connectivity will be greater in hypnotherapy compared to pharmacotherapy.

Statistical Analysis of 2.1 Normative controls vs. urgency incontinence subjects: Regions of interest containing the insula and anterior cingulate cortex will be analyzed in keeping with our a priori hypothesis using two way ANCOVA with group as the between subject's factor and age as a covariate. Pre-treatment β weights for both bladder filling and urgency regressor effect on anterior cingulate cortex and insula signal among normative subjects will be compared to the effect on signal in urgency incontinence subjects. The planned study size allows detection of differences between groups with an effect size >0.8 with power of 0.8, smaller than the observed effect size in our pilot study.⁴³ The effect size observed in our pilot study (Cohen's d ranged from 0.8 to 1.5) suggests that the study will be adequately powered (greater than 0.8) to reject the null hypothesis at an alpha=0.05. In addition to analysis of prior regions of interest, group wise whole brain contrast will also be performed using an identical statistical model. False positives will be corrected at a significance threshold corresponding to p <.005 applied in combination with a minimum cluster size threshold of 32 native voxels (p < 0.05), parameters derived from 10,000 Monte Carlo simulations.⁸⁰ Analysis of between group differences in functional connectivity will be performed in a similar fashion to that used to analyze brain activation evoked by bladder filling and emptying. The large observed effect size in our preliminary data (>3) suggests that the sample size used for proposed analysis of evoked potentials will be more than adequate.

Although the principal purpose of this analysis is to further explore the pathophysiologic underpinnings of UUI within the brain, we will also explore the use of evoked potentials and functional connectivity as a biomarker for UUI. Towards that end we will construct receiver operator curves (ROCs) based on fMRI output from controls and patients with UUI.

Statistical Analysis 2.2 Pre- and Post-Treatment measurements in patients with UUI: Efficacy of hypnotherapy and pharmacotherapy on anterior cingulate cortex and right insula activation will be compared using a 2x2 (Group x Time) mixed model ANCOVA to correct for potential differences in group characteristics (e.g. age). Analysis of treatment effect will be focused on the anterior cingulate cortex and insula based on preliminary data that suggests the effect size for change in activation will be highest in these regions. Prior functional MRI analysis during the hypnotic state has shown complete suppression of anterior cingulate cortex activation in response to pain.⁵⁵ However, the magnitude of suppression of anterior cingulate cortex or insula signal outside the hypnotic state has not been studied. Current study size will be able to detect differences between pre and post treatment signal within a treatment group with an effect size of approximately 0.5 and a power of 0.8. Minimal effect size would be approximately equivalent to a 60% decrease in the excess (above normative control) anterior cingulate cortex and insula signal. We predict a main effect of time, suggesting that both treatments are effective in reducing activity within the anterior cingulate cortex and insula. However, we also predict a significant Group x Time interaction, indicating that that change in activity will be greater for the hypnotherapy relative to the pharmacotherapy group. Minimum detectable effect size for the Group X Time interaction is 0.7 with power of 0.8 and alpha of 0.05. Simple effects tests will also be conducted to ensure that randomization to treatment arm was successful (i.e. no differences in baseline activity across the two groups).

Similar analyses will be conducted to evaluate the effect of treatment on functional connectivity. No prior data is available in the literature regarding the expected change in waking state connectivity following hypnotherapy. Current study size will be able to detect within-group differences between pre and post treatment signal with a minimal effect size of approximately 0.5 and a power of 0.8, much lower than the observed effect size of >3 in our pilot study. The minimum effect size would be reached with a 15% decrement in anterior cingulate cortex to insula connectivity. As for evoked activity we predict both a main effect of time, and predict a significant Group x Time interaction, indicating that change in functional connectivity will be greater for the hypnotherapy relative to the pharmacotherapy group. Minimum detectable effect size for the Group X Time interaction is 0.7 with power

of 0.8 and alpha of 0.05. This minimum effect size will be reached when between group differences in anterior cingulate cortex to insula connectivity are \geq 30%.

The principal purpose of this analysis will be to explore the mechanism of action of hypnotherapy when used to treat UUI, using pharmacotherapy as a control treatment that is not expected to exert its therapeutic effect via the brain. In addition we will explore the utilization of evoked activity and functional connectivity as biomarkers by correlating changes in these fMRI parameters with physiologic outcome measures, specifically UUI episodes. We understand that there is currently insufficient literature to determine the optimal method of assessing this correlation in the setting of a non-inferiority study design, and will look towards OCRA guidance on this aspect of the analytic plan in the future.

Anticipated/Expected Outcomes: Results from this study should confirm the differences between normative and urgency incontinence subjects with respect to limbic system evoked activation and functional connectivity. Confirmation of abnormal functional connectivity in urgency incontinence subjects during the resting state would be a particularly important contribution to the study of functional disorders in general. Abnormal resting connectivity data does not require that data be acquired and temporally linked to a performance of a task while in the MRI scanner making data acquisition less technically demanding. Abnormal resting connectivity has thus far only been observed in fibromyalgia but if shown to be more widely present among functional disorders could prove a diagnostic tool and/or target of new therapies. Demonstration that hypnotherapy's impact on brain activation and connectivity extends past the hypnotic state and persists during wakefulness would allow treatment effects of hypnotherapy, and perhaps other mind/body therapies, to be assessed temporally distant from the time of therapy. The delayed assessment should give much better insight into the likelihood of a durable clinical benefit for the patient. Demonstration that hypnotherapy has greater impact on functional MRI findings than pharmacotherapy would argue that resultant brain plasticity is related to mind-body therapy rather than due to altered sensory input (from the bladder).

10. Data Collection and Quality Assurance

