9.2 Sample Size and Randomization

Power Analysis/ Sample Size Calculation for Clinical RCT Specific Aim 1: We performed sample size calculations for change in UUI episodes and change in OABq-SF scores based on our pilot data & urgency incontinence literature.^{11,16,52} The study design will use a non-inferiority design to compare the primary outcome (change in UUI episodes in the hypnotherapy versus pharmacotherapy groups). With respect to the outcome variable of percent reduction in UUI episodes as determined by bladder diaries, we will use a one-sided noninferiority test at level alpha = 0.25 and a non-inferiority margin of 5%. If μ_h is the population mean percent reduction in incontinent episodes for the hypnotherapy group, and μ_m is the population mean percent reduction in incontinent episodes for the medications group, we will then test $H_0: \mu_h - \mu_m \le -5$ against the one-sided alternative $H_A: \mu_h - \mu_m > -5$ using significance level 0.025. If the null hypothesis is rejected then we may conclude hypotherapy is not inferior to medication therapy, on average, by more than 5%, and in fact may be superior to medication therapy, with respect to percent reduction in incontinent episodes. The test may be performed by computing the lower 97.5% one-sided confidence bound for $\mu_h - \mu_m$. If the lower confidence bound exceeds -5% we will conclude non-inferiority of hypnotherapy. Should that lower bound exceed zero we will conclude superiority. Assuming a subject drop-out, withdrawal and missing data rate as high as 33%, 52 subjects will be available for analysis in both hypnotherapy and medications groups. If $\mu_h - \mu_m \ge 9\%$, this sample size would provide power ≥ 80% for the non-inferiority test. Rigorous efforts will be made to reach an achieved attrition rate of 20-25%, such that approximately 60 subjects would be available for analysis in each group. This would allow for detecting non-inferiority if the actual $\mu_h - \mu_m \ge 8$ %. If the attrition rate at 1 year follow-up is < 20%, randomization of 152 subjects will allow us to detect even smaller inter-group differences than quoted previously.

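### The primary count model allows for excess zeros but names no overdispersion term, so the deciding interval would be too narrow if a woman's counts vary between visits more than Poisson allows

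*Combined protocol and SAP*

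**What the plan says.** Section 9.6 (Specific Aim 1) sets the primary model: "we will use a zero inflated Poisson (ZIP) generalized linear mixed model for the analysis". The reason given is low counts with many zeros. There are two branches.

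- **Zeros inflated:** the interval for percent change combines the two parts of the model, with a delta-method standard error that a bootstrap is to check.
- **Zeros not inflated:** "If there is no inflation at 0, i.e. standard Poisson regression is appropriate", and the exponentiated group effect gives the percent change. No bootstrap is mentioned here.

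The section does not say what the random effects are. It names no negative binomial model, scale parameter, observation-level effect or robust variance. It gives no resampling unit and no rule for the case where bootstrap and delta method disagree. Section 9.3 adds parametric mixed and semi-parametric longitudinal models, but only to explore differences over time.

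Section 9.2 sets the decision rule: "The test may be performed by computing the lower 97.5% one-sided confidence bound for" the difference in mean percent reduction, and "If the lower confidence bound exceeds -5% we will conclude non-inferiority of hypnotherapy". A bound above zero leads to a claim of superiority.

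**The concern.** Zero inflation and overdispersion are different departures from Poisson. Counts can show no excess of zeros and still vary more than their mean, so the condition in the second branch does not justify the Poisson variance. The zero-inflated branch has the same gap, because its count part is still Poisson.

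A subject random intercept absorbs stable differences between women. It does not absorb extra variation between one woman's diaries at different visits, and that variation drives the error of a change from baseline. The plan itself gives reasons to expect women to respond unevenly:

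- expectations are anticipated to predict improvement, and hypnotic susceptibility is tested as a predictor (Section 9.6);
- baseline severity is called a risk factor for treatment failure (Section 9.2);
- about 30% drug non-compliance or withdrawal is cited (Section 5.4), and non-compliant women stay in the intention-to-treat analysis (Section 9.3).

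An understated standard error raises the lower bound, so non-inferiority and superiority both become too easy to declare.

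**Working it through.** **1. The plan's own figures.** Section 9.2 states "52 subjects will be available for analysis in both hypnotherapy and medications groups" and, for a true difference of +9 points, "this sample size would provide power ≥ 80% for the non-inferiority test"; about 60 per arm is tied to +8. No SD is given. With n = 2 × SD² × (1.960 + 0.842)² / (difference + 5)², an SD of 25.4 gives 2 × 645.16 × 7.851 / 14² = 51.7, so 52, and the same numerator / 13² = 59.9, so 60 (power 0.803 and 0.801). The two statements therefore agree with each other at one-sided 0.025. Section 9.2 also prints "at level alpha = 0.25 and a non-inferiority margin of 5" beside "using significance level 0.025". At 0.25 the power would be 0.98, so 0.25 reads as a misprint. This calculation treats percent reduction as continuous and says nothing about count dispersion.

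**2. Analytic link.** If the true variance of the estimate is φ times the model's variance, one-sided error = Φ(-1.96/√φ).

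- φ = 1.5: Φ(-1.600) = 5.5%
- φ = 1.85: Φ(-1.441) = 7.5%
- φ = 2.90: Φ(-1.151) = 12.5%
- φ = 4: Φ(-0.980) = 16.4%

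**3. Simulation at the non-inferiority boundary.** From the documents: 52 per arm, visits at 0, 2, 6 and 12 months, margin 5 points, one-sided 2.5%. Assumed: baseline mean 8 or 5 per 3-day diary, subject log-SD 0.6, 25% structural zeros at follow-up, and each visit's mean multiplied by a gamma variable with mean 1 and variance d (d = 0.25 is a 50% coefficient of variation). The fitted model was a random-intercept ZIP with a delta-method bound, 1,000 runs per cell, Monte Carlo SE about 0.5 to 1.3 points. One-sided error in percent:

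| Scenario | d=0 | 0.1 | 0.25 | 0.5 | 1.0 |
|---|---|---|---|---|---|
| Mean 8, reductions 70% v 65% | 2.3 | 6.8 | 8.9 | 14.2 | 20.6 |
| Mean 5, reductions 70% v 65% | not run | not run | 5.6 | 10.1 | 15.0 |
| Mean 8, reductions 55% v 50% | not run | not run | 11.6 | 16.3 | 22.1 |

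Cross-check with step 2 in the first row: at d = 0.25, φ = (0.0834/0.0550)² = 2.30, giving Φ(-1.292) = 9.8% against 8.9% simulated. At d = 0.5, φ = (0.1004/0.0562)² = 3.19, giving 13.6% against 14.2%.

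**4. What the diary reliability implies.** Section 9.1 gives the diary an ICC of .76. For baseline mean m and subject log-SD s, two diaries from one woman have ICC = m²(e^{s²} - 1) / [m²(e^{s²} - 1) + m + d·m²·e^{s²}]. With m = 8 and s = 0.7 this is 40.5 / (40.5 + 8 + 104.5d): 0.83 at d = 0, 0.54 at 0.25 and 0.40 at 0.5. Solving for .76 gives d = (40.5/0.76 - 48.5)/104.5 = 0.046, about 0.05. For s from 0.6 to 1.0 and m from 5 to 8, the answer runs from 0 to 0.15.

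**5. Simulation under no arm difference.** Inputs: baseline mean 8, follow-up mean 3.2, 20% structural zeros, s = 0.7, 52 per arm. In 400 trials per scenario the ZIP error was 1.9% at d = 0, 3.0% at 0.05, 4.3% at 0.1, 8.4% at 0.25 and 11.8% at 0.5. At baseline mean 5 it was 2.8% (0.05), 3.5% (0.1) and 5.6% (0.25). This null is zero difference, so these are superiority errors rather than non-inferiority errors.

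**6. Uneven response in the Poisson branch.** Inputs: 52 per arm, baseline and one follow-up, within-woman Poisson SE, no arm difference, baseline mean 5 or 8, reduction 50% or 65%, 20,000 trials per case. With between-woman response as the only added variation, error was 2.4-2.8% at response log-SD 0, 5.4-8.0% at 0.5 and 8.7-13.8% at 0.7.

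**7. Remedies in the step 3 design.** A zero-inflated negative binomial mixed model gave 1.8-4.6%. ZIP with a subject-level sandwich SE gave 2.4-4.1%. The subject-bootstrap SE was 0.96, 1.49, 1.88 and 2.56 times the delta-method SE at d = 0, 0.25, 0.5 and 1.0 (15 datasets each).

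**The case against.** A reader might infer that the planned interval is simply too narrow, or that type I error is three to five times nominal. The documents support neither. With no visit-level overdispersion the ZIP model holds its level. The documents give no dispersion, and over the values tried the rise runs from none to about nine-fold (22.1/2.5 = 8.8).

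The one reliability figure in the documents points to the low end: an ICC of .76 fits dispersion of about 0.05, and the larger scenarios imply much less repeatable diaries. A baseline mean of 8 is also unsupported. Section 9.6 expects low counts, and at mean 5 and dispersion 0.25 the error is 5.6%, not 8.9%. Nor can one say that the model lacks the needed term: a mixed model is named and its random effects are left open. Finally, the bootstrap check sits in the branch the plan expects, and if it resampled women it would expose the problem.

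Most of this stands, and it limits the size of the point. It does not remove it. Section 9.1 does not say which diary variable the ICC covers, and repeatability in stable women does not cover uneven response after treatment starts. At dispersion 0.1, inside the range compatible with the ICC, the boundary simulation at mean 8 already gave 6.8%. The bootstrap has no stated resampling unit, no authority over the decision and no place in the Poisson branch. The remedies are not exactly nominal either: the negative binomial model reached 4.6% in one scenario. They are nonetheless closer to nominal than ZIP with the delta method in every overdispersed case.

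**Conclusion.** The point holds conditionally. The step from no excess zeros to a valid Poisson variance is wrong, and the plan leaves the random effects, the treatment of overdispersion and the deciding interval unspecified for its primary test. The interval is too narrow if two things are true together: the only random effect is a subject intercept, and counts vary between visits, including through uneven response, more than Poisson allows.

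The likely range under assumed inputs runs from almost no effect (about 3% at dispersion 0.05, no-difference null) to about 6-16% at dispersion 0.25-0.5 at the non-inferiority boundary, against 2.5%. These figures rest on assumed baseline means, zero fractions, subject variation and dispersion, so they illustrate sensitivity and do not estimate this trial's error rate. The gap should be closed before unblinding.

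**What to change.** In Section 9.6, define the random effects and then do one of the following.

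- Make a negative binomial mixed model with a subject random effect, zero-inflated if needed, the primary model. Poisson is its limiting case, so no preliminary choice between variances is required.
- Keep ZIP or Poisson, but state that a subject-level bootstrap or subject-clustered robust interval decides the primary test in both branches, with women as the resampling unit. This also covers response differences that persist across visits.

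Correct the 0.25 in Section 9.2 at the same time.

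The cost is SAP wording, standard code and slightly more analysis work. The interval hardly changes without overdispersion: in the mean 8, 70% v 65% scenario the negative binomial SE was 5.36 points against 5.29 for ZIP. It widens when overdispersion is present (6.40 against 5.35 at dispersion 0.1; 7.76 against 5.50 at 0.25). Power would then be lower than the ZIP interval suggests, but that reflects the real uncertainty.

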9.51 Primary Outcome

Specific Aim 1: Determine whether a mind/body therapy (hypnotherapy) is as, or is more effective and durable, in treating urgency urinary incontinence (UUI) than a non-mind/body treatment (pharmacotherapy)

The primary outcome for the analysis of Objective 1 will be change in UUI episodes based on 3 day voiding diaries for the hypnotherapy group compared to the pharmacotherapy group at 2 month follow-up (See flow Diagrams Section 5. "Study Interventions")

Specific Aim 2: Determine whether hypnotherapy treatment of UUI (urgency urinary incontinence) is associated with greater modification of brain activation and connectivity on functional MRI than that which occurs following pharmacotherapy.

Hypothesis 2.2. Among patients with urgency incontinence, hypnotherapy will decrease hyper-activation of the limbic cortex in response to bladder distension and/or modulate functional connectivity within the limbic system. Moreover, normalization of hyper-activation and connectivity will be greater in hypnotherapy compared to pharmacotherapy

The primary outcome is to evaluate whether UUI subjects treated with hypnotherapy have decreased hyperactivation of the limbic cortex (ACC and insula) in response to bladder distention and/or modulation in functional connectivity within the limbic cortex in response to bladder distension compared to subjects treated with pharmacotherapy. This will be obtained after the subjects finish their 8 weeks of either pharmacotherapy or hypnotherapy (Visit 12; see flow Diagrams Section 5. "Study Interventions')

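### Without zero inflation, section 9.6 takes percent change from a between-arm ratio, but the −5 margin in 9.2 is on a difference in percent reductions, a contrast that 9.6 never states

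*Combined protocol and SAP*

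**What the plan says.** Section 9.2 gives a full decision rule. It defines μ_h with the words "is the population mean percent reduction in incontinent episodes for the hypnotherapy group", defines μ_m likewise for medication, and tests μ_h − μ_m one-sided at 0.025 through a lower 97.5% bound: "If the lower confidence bound exceeds -5% we will conclude non-inferiority of hypnotherapy". If the bound also exceeds zero, superiority is concluded.

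Section 9.51 names the primary outcome as "change in UUI episodes based on 3 day voiding diaries for the hypnotherapy group compared to the pharmacotherapy group" at 2 months, and 9.6 repeats that "The primary outcome measure will be change in UUI episodes from baseline to follow-up with a between group comparison". Neither says on which scale the change is measured.

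Section 9.6 (Specific Aim 1) warns that "Simple conversion to percent change will not correct the discrete nature of the data", rules out standard least squares, and chooses a zero-inflated Poisson mixed model for the counts. It then splits into two cases:

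- No inflation at zero: "the associated log-linear model yields percent change as a natural parameter (by exponentiating the group effect".
- Inflation present: "If there is significant inflation at 0, the confidence interval for percent change in the mean will be constructed" by combining the two parts of the model, with a delta-method standard error checked by bootstrap. No test or level decides when inflation counts as significant.

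It adds: "We will be able to derive mean UUI episodes as well as mean % change in UUI episodes following ZIP model analyses". The Aim 1 text of 9.6 does not mention non-inferiority, the −5 margin, μ_h − μ_m or the 97.5% bound.

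**The concern.** The margin has a meaning only on the scale on which it was set. In a log-linear model the exponentiated group effect compares the arms multiplicatively; it is not one arm's percent reduction minus the other's. An analyst who follows 9.6 to the letter in the case without zero inflation therefore holds an estimate to which the 9.2 rule does not apply directly. In the other case the analyst holds an interval that may be within or between arms.

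The primary non-inferiority conclusion is at stake. A conversion left open could be chosen with the results in view, because 9.5 places the analysis after the blind is broken. Moreover, the branch that determines the scale is itself chosen from the data by an unnamed criterion.

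**Working it through.** **Inputs.** From 9.2: margin −5 points on μ_h − μ_m; one-sided 0.025; 52 per arm at a true difference of 9 points, and about 60 per arm at 8 points, the first with at least 80% power. From 9.6: the exponentiated group effect. Not in the documents: the standard deviation and the medication-arm percent reduction P. I assume a range for P.

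**1. The scale of the plan's sizing.** Since no SD is given, solve for it:

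SD = (true difference + 5) / ((1.96 + 0.84) × √(2/n))

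- n = 52: 14 / (2.80 × √(2/52)) = 25.5
- n = 60: 13 / (2.80 × √(2/60)) = 25.4

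With SD 25.4 the formula returns 52 and 60 per arm, with power 80.2% and 80.0%. The two scenarios agree with each other as a test of a difference of means. Because the SD is back-solved, this shows consistency and is not an independent reproduction. It also takes alpha as 0.025, which matches the 97.5% bound. Section 9.2 prints 0.25 once as well, and that value would give an SD of about 47 in both scenarios.

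**2. What the exponentiated effect measures.** Let P_h and P_m be the percent reductions in arm means. A group-by-time effect exponentiates to the ratio of ratios (100 − P_h)/(100 − P_m). A group effect on the 2-month means gives the same quantity if the baseline means are equal. Neither equals P_h − P_m.

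**3. Converting the margin.** Setting P_h = P − 5, with P the medication-arm reduction, the ratio (hypnotherapy over medication) that corresponds to −5 points is (100 − P + 5)/(100 − P). Conversely, a ratio limit of 1.05 allows a deficit of only 0.05 × (100 − P) points.

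| Assumed P (%) | Ratio equal to −5 points | Deficit allowed by ratio 1.05 (points) |
|---|---|---|
| 20 | 85/80 = 1.06 | 4.0 |
| 30 | 75/70 = 1.07 | 3.5 |
| 40 | 65/60 = 1.08 | 3.0 |
| 50 | 55/50 = 1.10 | 2.5 |
| 60 | 45/40 = 1.13 | 2.0 |
| 70 | 35/30 = 1.17 | 1.5 |
| 80 | 25/20 = 1.25 | 1.0 |

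The two scales agree only at P = 0, where 105/100 = 1.05.

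**4. The same ratio, different answers.** An upper bound of 1.10 on the ratio corresponds to a deficit of 0.10 × (100 − P) points: 8 at P = 20%, 6 at 40%, 4 at 60% and 2 at 80%. The first two lie outside the margin and the last two inside.

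**5. A point-estimate illustration.** Assume reductions of 70% on medication and 66% on hypnotherapy. The difference is −4 points, inside the margin. The ratio is 34/30 = 1.13, well beyond 1.05.

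**The case against.** The best reply is that 9.2 already holds the complete rule, so 9.6 need not repeat it. Section 9.6 supplies the estimation side: mean percent change can be derived from the model, with a delta-method interval and a bootstrap check. Read together, the natural path is arm-level percent change, then the difference, then the 9.2 bound. The plan also expects excess zeros, so the ratio remark covers the less expected case. Much of this stands. It shows that the link is easy to make, but no sentence makes it, and the one explicit recipe for the case without inflation gives a ratio.

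Two stronger readings are tempting, and the documents support neither.

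- A reader might infer that the −5 rule cannot be applied at all, or that a post-hoc conversion is inevitable. If the model contains arm and time, the same fit yields arm-level means in either case. The contrast can also be programmed before unblinding, which 9.2 delays until 12-month follow-up and data checks are complete. The post-hoc choice is a risk that the wording leaves open.
- A reader might infer that the trial is underpowered, because individual percent reductions are erratic in women with few baseline episodes. The plan gives neither the mix of baseline counts nor an SD. Stratification also provides for women with 4 or more episodes, whose values are steadier. The wording of 9.6 points to the reduction of the mean, not to an average of individual reductions. Setting individual-level SDs against a back-solved 25.4 would therefore prove nothing.

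**Conclusion.** The concern holds as a mismatch of scale and a missing contrast, and it should be fixed. Without zero inflation, the stated source of percent change is a between-arm ratio that does not fit the stated rule. With zero inflation, the contrast and its bound are left to inference, and the criterion that separates the two cases is unnamed. Section 9.2 also leaves open whether μ averages individual reductions or is the reduction of the arm mean.

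For medication-arm reductions of 20 to 80%, −5 points equals a ratio of 1.06 to 1.25. Reading 5% on the ratio would be stricter, allowing a deficit of only 4.0 down to 1.0 points. These figures rest on the assumed reductions and, for a ratio of 2-month means, on equal baseline means. Under the same conditions a difference of zero is a ratio of one, so the mismatch bears on the non-inferiority margin and not on the null value for superiority. Nothing here shows that the sample size is inadequate.

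**What to change.** In 9.6, stop using the exponentiated group effect as the source of percent change for the primary test, and state one contrast for both cases:

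1. Fit the count model with arm, time and arm-by-time, plus the zero-inflation part if used.
2. Derive each arm's percent reduction in mean episodes from baseline to 2 months, averaging predictions over the observed covariates and the random effects. The averaging must be stated because 9.6 adds expectation, hypnotic susceptibility and possibly other covariates to a mixed model.
3. Take the difference μ_h − μ_m and compare its one-sided 97.5% lower bound (delta method, checked by bootstrap) with −5 points, identically with or without zero inflation.

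In 9.2, define μ as the percent reduction of the arm mean, which matches the wording of 9.6 for the zero-inflated case. Fix all of this before unblinding.

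The cost is a few sentences in 9.2 and 9.6 and a little programming; the delta-method and bootstrap steps are already planned for the zero-inflated case. The drawback is that the power figure in 9.2 has to be checked on this scale. Trial conduct does not change.
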